7.1.3 Guidelines for Evaluation of Measurable Disease

All measurements should be recorded in metric notation, using calipers if clinically assessed. All baseline evaluations should be performed as close as possible to the treatment start and never more than 4 weeks before the beginning of the treatment.

The same method of assessment and the same technique should be used to characterize each identified and reported lesion at baseline and during follow-up. Imaging based evaluation should always be done rather than clinical examination unless the lesion(s) being followed cannot be imaged but are assessable by clinical exam.

Clinical lesions: Clinical lesions will only be considered measurable when they are superficial and $>10\text{mm}$ diameter as assessed using calipers (e.g. skin nodules). For the case of skin lesions, documentation by color photography including a ruler to estimate the size of the lesion is suggested. As noted above, when lesions can be evaluated by both clinical exam and imaging, imaging evaluation should be undertaken since it is more objective and may also be reviewed at the end of the study.

Chest X-ray: Chest CT is preferred over chest X-ray, particularly when progression is an important endpoint, since CT is more sensitive than X-ray, particularly in identifying new lesions. However, lesions on chest X-ray may be considered measurable if they are clearly defined and surrounded by aerated lung.

CT, MRI: CT is the best currently available and reproducible method to measure lesions selected for response assessment. This guideline has defined measurability of lesions on CT scan based on the assumption that CT slice thickness is 5mm or less. When CT

scans have slice thickness greater than 5 mm, the minimum size for a measurable lesion should be twice the slice thickness. MRI is also acceptable in certain situations (e.g. for body scans).

Ultrasound: Ultrasound is not useful in assessment of lesion size and should not be used as a method of measurement. Ultrasound examinations cannot be reproduced in their entirety for independent review at a later date and, because they are operator dependent, it cannot be guaranteed that the same technique and measurements will be taken from one assessment to the next. If new lesions are identified by ultrasound in the course of the study, confirmation by CT or MRI is advised. If there is concern about radiation exposure at CT, MRI may be used instead of CT in selected instances.

Endoscopy, laparoscopy: The utilization of these techniques for objective tumor evaluation is not advised. However, they can be useful to confirm complete pathological response when biopsies are obtained or to determine relapse in trials where recurrence following complete response or surgical resection is an endpoint.

Tumor markers: Tumor markers alone cannot be used to assess objective tumor response. If markers are initially above the upper normal limit, however, they must normalize for a patient to be considered in complete response. Because tumor markers are disease specific, instructions for their measurement should be incorporated into protocols on a disease specific basis. Specific guidelines for PSA response (in recurrent prostate cancer), have been published

Cytology, Histology: These techniques can be used to differentiate between PR and CR in rare cases if required by protocol (for example, residual lesions in tumor types such as germ cell tumors, where known residual benign tumors can remain). When effusions are known to be a potential adverse effect of treatment (e.g. with certain taxane compounds or angiogenesis inhibitors), the cytological confirmation of the neoplastic origin of any effusion that appears or worsens during treatment can be considered if the measurable tumor has met criteria for response or stable disease in order to differentiate between response (or stable disease) and progressive disease.

7.2 Response Criteria for RECIST 1.1 subjects with measurable disease

7.2.1.1 Evaluation of Target Lesions

Complete Response (CR): Disappearance of all target lesions, determined by two separate observations conducted not less than 4 weeks apart. There can be no appearance of new lesions.

Partial Response (PR): At least a 30% decrease in the sum of the longest diameter (LD) of target lesions, taking as reference the baseline sum LD. There can be no appearance of new lesions.

Progressive Disease (PD): At least a 20% increase in the sum of the LD of target lesions, taking as reference the smallest sum LD recorded since the treatment started, or the appearance of one or more new lesions.

Stable Disease (SD): Neither sufficient shrinkage to qualify for PR nor sufficient increase to qualify for PD, taking as reference the smallest sum LD since the treatment started.

7.2.1.2 Evaluation of Non-Target Lesions

Complete Response (CR): Disappearance of all non-target lesions and normalization of tumor marker level.

Incomplete Response/Stable Disease (SD): Persistence of one or more non-target lesion(s) and/or maintenance of tumor marker level above the normal limits.

Progressive Disease (PD): Appearance of one or more new lesions and/or unequivocal progression of existing non-target lesions.

7.2.1.3 Evaluation of Best Overall Response

The best overall response is the best response recorded from the start of the treatment until disease progression/recurrence (taking as reference for progressive disease the smallest measurements recorded since the treatment started). The patient's best response assignment will depend on the achievement of both measurement and confirmation criteria.

Target Lesions	Non-Target Lesions	New Lesions	Overall Response	Best Response for this Category Also Requires:
CR	CR	No	CR	≥4 wks. confirmation
CR	Non-CR/SD	No	PR	≥4 wks. confirmation
PR	Non-PD	No	PR	
SD	Non-PD	No	SD	documented at least once ≥4 wks. from baseline
PD	Any	Yes or No	PD	no prior SD, PR or CR
Any	PD*	Yes or No	PD	
Any	Any	Yes	PD	
* In exceptional circumstances, unequivocal progression in non-target lesions may be accepted as disease progression.				

Note: Patients with a global deterioration of health status requiring discontinuation of treatment without objective evidence of disease progression at that time should be reported as “symptomatic deterioration”. Every effort should be made to document the objective progression even after discontinuation of treatment.
				

Note: If subjects respond to treatment and are able to have their disease resected, the patient's response will be assessed prior to the surgery.

[figure not shown]
7.2.2 PSA Response

Per PCWG3 criteria, PSA response rate will be defined as the proportion of subjects who have a PSA response defined by a 50% decline or more in PSA (ng/ml) from baseline measured twice at least 3 weeks apart. Based on the PCWG3 criteria, a favorable effect on PSA may be delayed for ≥ 12 weeks. PSA will be monitored every cycle, but treatment will be planned to continue through early rises for 12 weeks unless other evidence of progression, such as radiographic progression. Therefore, early rises in PSA before 12 weeks will not be considered progression when determining PSA response.

7.2.3 PSA Progression by PCWG3 criteria

PSA evidence for progressive prostate cancer consists of a PSA level of at least 1 ng/ml which has risen

on at least 2 successive occasions, at least one week apart. If the third PSA (#3) value is less (i.e., #3b) than the screening PSA (#2) value, then an additional test for rising PSA (#4) will be required to document progression by PSA. All PSA progression as above will require confirmation of equal or higher PSA value at least 4 weeks later (from the #3a or #4 value as applicable). **Based on the PCWG3 criteria, a favorable effect on PSA may be delayed for ≥ 12 weeks. PSA will be monitored every cycle, but treatment will be planned to continue through early rises for 12 weeks unless other evidence of progression, such as radiographic progression. Therefore, early rises in PSA before 12 weeks will not be considered progression when determining PSA progression by PCWG3 criteria without evidence of other progression.**

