3.1 Inclusion Criteria

- 3.1.1 Ability to understand and voluntarily agree to participate by providing written informed consent for the trial.
- 3.1.2 Histologically confirmed prostate adenocarcinoma cancer, either pure or mixed. Small cell/neuroendocrine differentiation is not allowed.
- 3.1.3 Castrate levels of serum testosterone (≤ 50 ng/dL). Patients must continue androgen deprivation therapy with an LHRH analogue or antagonist if they have not undergone bilateral orchectomy.
- 3.1.4 Patients must have metastatic disease; either non-measurable disease OR measurable disease per RECIST 1.1.
- 3.1.5 Progressive disease despite ongoing treatment with Androgen Deprivation Therapy (ADT) based **on ANY one of the following**:
 - 1) Progression on axial imaging per treating investigator
 - 2) PSA evidence for progressive prostate cancer consists of a PSA level of at least 1 ng/ml which has risen on at least 2 successive occasions, at least one week apart. If the confirmatory PSA (#3) value is less (i.e., #3b) than the screening PSA (#2) value, then an additional test for rising PSA (#4) will be required to document progression for the purposes of eligibility.

- 3) Radionuclide bone scan: At least two new foci consistent with metastatic lesions
- 3.1.6 Patients treated with first generation anti-androgen as most recent systemic therapy (e.g. bicalutamide, nilutamide) must have at least 4 weeks elapsed from treatment discontinuation to start of protocol therapy with evidence of disease progression per criterion 3.1.5 *following* discontinuation of prior anti-androgen.
- 3.1.7 Minimum PSA at entry of 1 ng/mL is required.
- 3.1.8 ECOG Performance Status 0,1 or 2
- 3.1.9 Be ≥ 18 years of age on the day of signing informed consent.
- 3.1.10 Demonstrate adequate organ function as defined below:

System	Laboratory Value
Hematological	
ANC	$\geq 1,500/\mu\text{L}$
Platelets	$\geq 100,000/\mu\text{L}$
Hemoglobin	$\geq 9 \text{ g/dL}$ or $\geq 5.6 \text{ mmol/L}$ with or without a red blood cell transfusion within 2 weeks of enrollment
Renal	
Serum creatinine OR calculated creatinine clearance (GFR can also be used in place of creatinine or CrCl)	$\leq 1.5 \times \text{ULN}$ OR $\geq 30 \text{ mL/min}$ for subjects with creatinine levels $>1.5 \times$ institutional ULN
Hepatic	
Serum total bilirubin	$\leq 1.5 \times \text{ULN}$ OR Direct bilirubin $\leq \text{ULN}$ for subjects with total bilirubin levels $>1.5 \text{ ULN}$

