7.2.6 Progression-Free Survival

Progression-free survival (PFS) is defined as the duration of time from start of treatment to time of progression whether PSA progression by PCWG3 criteria (see section 7.2.3 above) and/or RECIST 1.1 criteria as applicable.

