11.2.2 Definition of Secondary Endpoints

The secondary endpoints of efficacy are radiographic progression-free survival time (rPFS) by PCWG3-modified RECIST 1.1, 30% PSA reduction from baseline, PSA progression-free survival time, duration of therapy (DOT), duration of PSA Response (DOR), progression-free survival time and overall survival time.

The secondary endpoints for safety and toxicity are adverse events as assessed by CTCAE criteria 5.0 and classified by body system, grade, and attribution. Other toxicity endpoints include intrapatient dose delays and dose reductions.

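### Section 7.2.3 reuses the entry rule for on-treatment PSA progression with no nadir and no minimum rise, so chance variation around a constant PSA of 1 ng/mL or more can meet it in about 35–50% of patients over a year of 3-weekly tests

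*Combined protocol and SAP*

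**What the plan says.** Section 7.2.3 opens with "PSA evidence for progressive prostate cancer consists of a PSA level of at least 1 ng/ml which has risen" and continues "on at least 2 successive occasions, at least one week apart". It then gives a clause for a falling third value: "If the third PSA (#3) value is less (i.e., #3b) than the screening PSA (#2) value", a further test (#4) is needed. Inclusion criterion 3.1.5(2) has the same trigger and nearly the same clause: "If the confirmatory PSA (#3) value is less (i.e., #3b) than the screening PSA (#2) value". The main change is one word, third in place of confirmatory.

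Section 7.2.3 adds two safeguards that the entry rule lacks:

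- Confirmation: "All PSA progression as above will require confirmation of equal or higher PSA value at least 4 weeks later", counted from the #3a or #4 value.
- Early rises: "early rises in PSA before 12 weeks will not be considered progression when determining PSA progression by PCWG3 criteria", unless there is other evidence of progression.

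It does not define value #1, name a nadir or baseline as reference, or set a minimum relative or absolute rise. Section 7.2.5, by contrast, takes the lowest on-treatment value as the reference for progression when it defines duration of response, whether by PSA or RECIST.

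PSA is measured every cycle, and a cycle is 21 days (sections 7.2.3 and 6.0). The rule feeds "PSA progression-free survival time" (section 11.2.2), time to PSA progression (section 11.6.2) and PFS, which section 7.2.6 ties directly to 7.2.3.

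**The concern.** At entry, the rule asks whether a PSA is rising in a patient already thought to be failing androgen deprivation, and a screening value exists to compare with. On treatment, the same rule is applied afresh at each 3-weekly visit for as long as the patient stays on. With no minimum rise, two upticks of any size start the count, and repeated testing gives chance many opportunities. A more precise assay does not help, because only the order of the values matters.

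The screening label has no clear on-treatment meaning. Two programmers could code different rules from the same text.

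At stake are the Kaplan-Meier estimates of PSA-PFS, time to PSA progression and PFS, and any exploratory biomarker comparison that uses PSA-PFS (section 11.6.3). The trial is single-arm, so no control group shares the error or reveals it.

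**Working it through.** The plan states no false-progression rate and no PSA variability, so there is no figure of its own to reproduce.

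**Inputs from the documents.** Trigger, 1 ng/mL floor, confirmation at 4 weeks or more, and week-12 exclusion (7.2.3); PSA every 21 days (7.2.3, 6.0); anticipated median therapy of 12 months (synopsis).

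**Assumptions.** True PSA constant and at least 1 ng/mL; independent, continuous visit-to-visit variation; visits at weeks 0, 3, …, 51; each new value compared with the preceding visits (a rolling reference, since value #1 is undefined). On a 3-weekly grid, the first visit at least 4 weeks later is 6 weeks later.

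**Step 1: one window.** With no minimum rise only ranks matter.

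- #3a path: four values must fall in one order, so P = 1/4! = 1/24 = 0.0417.
- #4 path (#2 above #1, #3 below #2, #4 above #2, then confirmed): 2 of 5! orders, so P = 2/120 = 1/60 = 0.0167.

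**Step 2: one year, approximate.** If every value must date from week 12 or later, there are 10 windows for #3a and 9 for #4. Treating windows as independent:

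- #3a only: 1 − (23/24)^10 = 0.347.
- Both paths: 1 − (23/24)^10 × (59/60)^9 = 0.438.

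**Step 3: one year, simulated.** This allows for overlapping windows (200,000 patients). Section 7.2.3 does not say which value the week-12 limit applies to, so three readings are shown.

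| What must date from week 12 | #3a only | #3a and #4 |
|---|---|---|
| All values | 34.6% | 43.1% |
| The rises | 37.4% | 46.4% |
| Triggering value only | 40.0% | 50.3% |

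The main reading is the last row, #3a only: about 40%. Both safeguards are already applied in every cell; with no confirmation the one-year figures are 89–99%.

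**Step 4: sensitivity.**

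- Value #2 read literally as the screening PSA: about 45%.
- Autocorrelated variation (AR(1), 0.3 to 0.9): 42–72%.
- Treatment ending at an assumed exponential median of 12 months: 21–33%.
- True level 0.8 ng/mL: 0–5% for CVs of 5–20%. At 0.3 ng/mL: 0%.
- PSA literally identical at every visit: 0%, because nothing rises.

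**Step 5: adding a minimum rise.** The two-rise trigger and the confirmation of at least 4 weeks are kept, and the triggering value must also be at least (1 + m) times the running nadir. One-year chance rate, #3a path, triggering value from week 12 (m and CV are assumptions):

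| Minimum rise m | CV 5% | CV 10% | CV 15% |
|---|---|---|---|
| 25% | 0.1% | 14% | – |
| 50% | – | 0.3% | 7% |

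If the two-rise trigger is instead dropped for a nadir threshold with one confirming value, a 25% threshold at CV 10% gives about 49–53%, depending on how the nadir and confirmation are coded. That is no better than the present rule.

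**The case against.** The strongest reply is that section 7.2.3 is not the bare entry rule: it adds confirmation and the week-12 exclusion. That is true, but the figures above already include both.

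A second reply is that the affected endpoints are secondary and descriptive, reported as Kaplan-Meier estimates with confidence intervals and no formal test. That stands and limits the consequence. The primary PSA response, rPFS, duration of therapy and OS do not use this rule.

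A third reply is that section 7.2.5 already supplies a lowest-value reference. It does so for duration of response, so a nadir is not absent from the plan. What stands is that the two sections disagree and must be reconciled.

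A reader might also infer more than the documents support:

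- *That any stable patient has a 40% chance of being called progressed.* The figure needs a true level of 1 ng/mL or more, ordinary variation and a full year of 3-weekly tests.
- *That the two-year rate, above 70%, describes this trial.* It assumes 3-weekly PSA for two years, whereas median therapy is expected to be 12 months and follow-up visits are every 12 weeks.
- *That duration of response suffers equally.* It applies only to responders. Many will be below their screening value; if #4 is then read as a third consecutive rise, the one-year chance rate is about 8%.
- *That any nadir rule cures the problem.* Step 5 shows otherwise.

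**Conclusion.** The concern holds for the definition of the endpoint. Section 7.2.3 is the entry rule with two safeguards added; it keeps a misplaced screening reference, leaves value #1 undefined, and sets no nadir and no minimum rise. Under a constant true PSA of 1 ng/mL or more, independent variation and a full year of 3-weekly tests, chance meets it in about 35–50%. Allowing for an assumed exponential end of treatment lowers this to about 21–33%. Neither range depends on the size of the variation while the level stays clear of the 1 ng/mL floor.

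The effect is to shorten PSA-PFS, time to PSA progression and PFS. Its size across the cohort depends on how many patients hold a plateau at or above 1 ng/mL, and for how long, which the documents do not give. The percentages are therefore chance rates for such a patient, not predicted rates for the 35. A reader might infer that the trial's efficacy conclusion is undermined; it is not, because the primary PSA response analysis does not use this rule. The point should be addressed but does not invalidate the design.

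**What to change.** Rewrite section 7.2.3 for on-treatment use, as an endpoint definition only:

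1. Keep the two successive rises, the confirmation at least 4 weeks later and the week-12 rule, and say which value the week-12 limit applies to.
2. Add a pre-specified minimum relative and absolute rise over the on-treatment nadir, or over baseline if PSA never fell.
3. Delete the reference to the screening PSA, define values #1 and #2, and state how the #4 path works.
4. Reconcile 7.2.3 with 7.2.5, so that one reference value governs PSA progression and duration of PSA response.
5. Choose the thresholds by simulation against a stated range of PSA variability, and report the chance rate.

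Because the existing conditions stay, a minimum rise can only remove false calls, not add them. Dropping the two-rise trigger for a bare nadir threshold does not have that property.

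The cost is one paragraph and a short simulation. No new data are needed, since PSA is already measured every cycle. The downside is that true progression may be dated somewhat later.

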7.2.4 Bone Scan

On bone scan, radiographic progression will be defined by PCWG3 criteria as ≥ 2 new bone lesions (Appendix B). However, for the first reassessment scan only, patients should remain on study and have a confirmatory scan performed 12 weeks later. If this confirmatory scan shows 2 or more additional new lesions, this defines progression. The date of progression is the date of the first reassessment bone scan. If the confirmatory scan does not show any additional new lesions, patient remains on study. If progression is observed on subsequent bone scans, a confirmatory scan is not required; the date of this bone scan is the date of progression (Appendix B).

7.2.5 Duration of Response

Duration of overall response: The duration of overall response is measured from the time measurement criteria are met for response (whether PSA response and/or RECIST 1.1 response when applicable) until the first date that recurrent or progressive disease is objectively documented (taking as reference for progressive disease the smallest measurements recorded since the treatment started).

The duration of overall CR is measured from the time measurement criteria are first met for CR until the first date that recurrent disease is objectively documented.

Duration of stable disease: Stable disease is measured from the start of the treatment until the criteria for progression are met, taking as reference the smallest measurements recorded since the treatment started.

7.2.6 Progression-Free Survival

Progression-free survival (PFS) is defined as the duration of time from start of treatment to time of progression whether PSA progression by PCWG3 criteria (see section 7.2.3 above) and/or RECIST 1.1 criteria as applicable.

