5.3 Concomitant Medications/Treatments

Medications or vaccinations specifically prohibited in the exclusion criteria are not allowed during the ongoing trial. If there is a clinical indication for any medication or vaccination specifically prohibited during the trial, discontinuation from trial therapy or vaccination may be required. The investigator should discuss any questions regarding this with the Study PI. The final decision on any supportive therapy or vaccination rests with the investigator and/or the subject's primary physician. However, the decision to continue the subject on trial therapy or vaccination schedule requires the mutual agreement of the investigator, the Sponsor and the subject.

Use of bisphosphonates/RANKL inhibitors are standard in CRPC and are allowed on the study.

Subjects are prohibited from receiving the following therapies during the Screening and Treatment of this trial:

- Antineoplastic systemic chemotherapy or biological therapy except for ongoing androgen deprivation therapy (e.g. with LHRH agonist/antagonist)
- Immunotherapy
- Chemotherapy not specified in this protocol
- Investigational agents
- 5 α -reductase inhibitors (e.g., finasteride, dutasteride).
- Any herbal product known to decrease PSA levels (eg. Saw Palmetto and PC-SPES)
- Neulasta[®]
- Radiation therapy
 - Local intervention is discouraged unless medically unavoidable. Radiation therapy to a symptomatic solitary lesion/area may be considered on a

case-by-case basis after consultation with the Principal Investigator (except during screening). Subjects receiving local intervention (e.g., palliative radiation) are allowed to continue to receive study treatment at the investigator's discretion. Subjects who receive local intervention may be considered not evaluable (and may be assigned a conservative censoring or progression date).

- Live vaccines within 30 days prior to the first dose of treatment and while participating in the trial. Examples of live vaccines include, but are not limited to, the following: measles, mumps, rubella, varicella/zoster, yellow fever, intranasal influenza, rabies, BCG (tuberculosis vaccine), and typhoid vaccine.
- Systemic glucocorticoids or other immunosuppressive drugs for any purpose other than to modulate symptoms from a drug-related AE of immunologic etiology (refer to Section 5.2 – Dose Modification). The use of physiologic doses of corticosteroids may be approved after consultation with the Study PI.

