7.1.2 Disease Parameters

Measurable disease. Measurable lesions are defined as those that can be accurately measured in at least one dimension (longest diameter in the plane of measurement is to be recorded) with a minimum size of:

- 10mm by CT scan (irrespective of scanner type) for studies with a slice thickness of \leq 5mm or twice the slice thickness or MRI
- 10mm caliper measurement by clinical exam (lesions which cannot be accurately measured with calipers should be recorded as non-measurable)
- 20mm by chest X-ray (if clearly defined and surrounded by aerated lung)

All tumor measurements must be recorded in millimeters (or decimal fractions of centimeters).

Malignant lymph nodes: To be considered pathologically enlarged and measurable, a lymph node must be \geq 15mm in short axis when assessed by CT scan (CT scan slice thickness recommended to be no greater than 5 mm). At baseline and in follow-up, only the short axis will be measured and followed.

Note: Tumor lesions that are situated in a previously irradiated area are not considered measurable.

Non-measurable disease. All other lesions (or sites of disease), including small lesions (longest diameter $<$ 20 mm with conventional techniques or $<$ 10 mm using CT scan), are considered non-measurable disease. Bone lesions, leptomeningeal disease, ascites, pleural/pericardial effusions, lymphangitis cutis/pulmonis, inflammatory breast disease, abdominal masses (not followed by CT or MRI), and cystic lesions are all non-measurable.

Target lesions. All measurable lesions up to a maximum of 2 lesions per organ and 5 lesions in total should be identified as **target lesions** and recorded and measured at baseline. Target lesions should be selected on the basis of their size (lesions with the longest diameter), be representative of all involved organ, but in addition should be those that lend themselves to reproducible repeated measurements.

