11.6.2 Secondary Objective Analyses

The time-to-event secondary endpoints of efficacy including rPFS, time to PSA progression, PSA progression-free survival time, DOT, DOR, PFS and OS will be analyzed using Kaplan-meier methods. Percentiles of each will be reported with associated 95% confidence intervals and a Kaplan-meier plot. The proportion of patients who are able to reach a 30% or greater PSA reduction from baseline will be reported with the associated 95% binomial confidence interval. Each of the above will be reported overall and by dose level during cycle 1.

Safety and toxicity will be described by dose level. Adverse events as assessed by CTCAE criteria 5.0 and classified by body system, grade, and attribution will be reported

using counts and proportions. Intrapatient dose delays and reductions will be described for each starting dose level.

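### PFS in 7.2.6 is time to progression: death is not an event and no general censoring rule is given; the bone-scan citation and the PSA reference value also need to be stated

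*Combined protocol and SAP*

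**What the plan says.** All references are to the combined protocol and SAP.

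- **PFS (7.2.6).** "Progression-free survival (PFS) is defined as the duration of time from start of treatment to time of progression whether PSA progression by PCWG3 criteria", with 7.2.3 cited for PSA, and/or RECIST 1.1 where applicable. Nothing follows on death or censoring. PFS is a secondary endpoint in 2.5.1 and 11.2.2, but it is not among the synopsis objectives or endpoints.
- **Other endpoints (11.2.2).** The section is titled as a definition. It opens "The secondary endpoints of efficacy are radiographic progression-free survival time (rPFS) by PCWG3-modified RECIST 1.1" and continues with names only.
- **Analysis (11.6.2).** "The time-to-event secondary endpoints of efficacy including rPFS, time to PSA progression, PSA progression-free survival time, DOT, DOR, PFS and OS" are to be analysed by Kaplan-Meier, with percentiles and 95% confidence intervals. No event or censoring rule is attached.
- **Censoring (5.3).** The one statement is "Subjects who receive local intervention may be considered not evaluable (and may be assigned a conservative censoring or progression date", and it concerns local intervention only.
- **Bone.** 7.1.2 places "Bone lesions, leptomeningeal disease, ascites" and other sites under non-measurable disease. Progression in 7.2.1.1 includes a 20% increase over "the smallest sum LD recorded since the treatment started, or the appearance of one or more new lesions"; in 7.2.1.2 it is "Appearance of one or more new lesions and/or unequivocal progression of existing non-target lesions". Section 7.2.4 differs: "On bone scan, radiographic progression will be defined by PCWG3 criteria as" at least two new lesions, with a confirmatory scan after the first reassessment scan and a dating rule.
- **PSA progression (7.2.3).** The text reuses the entry rule of 3.1.5: at least 1 ng/ml, two successive rises, and a fourth test if the third value is below the one labelled screening PSA (#2). It adds confirmation at least 4 weeks later, and it disregards rises before week 12 unless there is other evidence of progression.

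**The concern.** Kaplan-Meier needs an event rule and a censoring rule for each endpoint. Where 7.2.6 gives an event rule, it leaves out death, so a patient who dies without documented progression has no PFS event. Such a patient would have to be censored, and the estimate then treats the dead as if they shared the later progression risk of those still alive. The result is a time-to-progression estimate carrying the PFS label.

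For rPFS and PSA-PFS the analyst has only the names. Two analysts working from the same 35 patients could treat deaths, a single new bone lesion or a PSA series differently and report different medians. In a single-arm trial these estimates are read on their own, with no concurrent arm sharing the same choice.

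**Working it through.** The plan gives no PFS median, event count or power, so there is no figure to reproduce. The main check is of the text; the arithmetic is an illustration on assumed values.

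**1. Death and censoring.** The places that could supply a rule are:
- 7.2.6: progression only.
- 11.2.2: names only.
- 11.6.2: method only.
- 5.3: optional, for local intervention only, and open between censoring and progression.
- 5.7: follow-up to death or 24 months after treatment, so deaths are observed, but no endpoint rule.

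None makes death an event. None says how to censor patients who are event-free, start new therapy, miss assessments or are lost. Section 11.6.2 lists time to PSA progression and PSA progression-free survival as separate endpoints, so they were probably meant to differ. Death is the obvious candidate for the difference, but nothing written separates them.

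**2. Size of the death effect.** Assume constant hazards, a median of M months with deaths counted, and a share f of first events that are deaths without progression. The total hazard is ln 2 / M. Censoring deaths leaves (1 − f) × ln 2 / M, so the reported median is M / (1 − f).

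| M (assumed) | f = 5% | f = 10% | f = 20% |
|---|---|---|---|
| 6 | 6.3 | 6.7 | 7.5 |
| 12 | 12.6 | 13.3 | 15.0 |
| 18 | 18.9 | 20.0 | 22.5 |

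For M = 12: 12/0.95 = 12.63, 12/0.90 = 13.33, 12/0.80 = 15.00. A simulation of 400,000 patients gave 12.60, 13.37 and 14.99.

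For comparison, the exact 95% interval for a 12-month exponential median with an assumed 30 events is 2 × 30 × 12 = 720 divided by the chi-square quantiles on 60 degrees of freedom: 720/83.30 = 8.64 and 720/40.48 = 17.79 months. All three shifted medians lie inside it.

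**3. Bone lesions.** 7.2.6 cites 7.2.3 and plain RECIST 1.1. Read alone, that leads to 7.2.1, where one new lesion is progression and no exception is made for bone. 7.2.4 requires two or more and sets its own confirmation and date. For rPFS, the label PCWG3-modified RECIST 1.1 points to 7.2.4. For PFS, no such pointer exists.

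**4. PSA reference.** Take an assumed patient with screening PSA 100 ng/ml and, after week 12, values 5, 6 and 7.
- If #2 is the second value of the rising series (6), then 7 exceeds it and the two rises stand, subject to confirmation at least 4 weeks later.
- If #2 is the screening value (100), then 7 is below it and #4 is required. The text does not say whether #4 must exceed #3 or the screening value.

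Status and date can differ between the readings. The section also does not say whether the progression date is that of the first rise, the third value or the confirmation.

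**The case against.** - **Convention supplies death.** Many readers would add death to PFS without being told. But 7.2.6 is an explicit definition, and an explicit definition displaces convention. This reply does not remove the point.
- **Few deaths may be involved.** PSA is measured every cycle and PSA progression counts, so most patients may progress on record before dying. That is fair: the 20% share has no support in the documents and serves only as the upper end of a range.
- **Bone scans already have a rule.** This largely stands. A reader might infer that the plan contradicts itself on bone progression, or that rPFS has no bone rule. The documents do not support that: 7.2.4 deals specifically with bone scans, and a specific rule normally prevails over a general one. What remains is a missing citation in 7.2.6 and a missing exception in 7.2.1. The figure in Appendix B, which 7.2.4 cites, is not shown in this copy and is not counted against the plan.
- **7.2.3 is a workable PSA rule.** In part it is; the defect is the label #2 and what follows from it. A reader might infer that a calculable share of patients with stable PSA would be declared progressed. No such figure can be defended: the plan gives no PSA variability or trajectory, and the result depends on which later visit may confirm, which 7.2.3 leaves open. Nor does the ambiguity show that a nadir rule is the right one; that choice is the sponsor's.
- **The endpoints are minor.** They are secondary, untested and unpowered. This limits the severity, but not the need for a definition.

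**Conclusion.** The point holds, and it should be corrected before analysis. As written, PFS is time to progression, and rPFS and PSA-PFS have no stated event or censoring rule. This rests on the text alone, and confidence is high. The bone issue is a missing cross-reference, and the PSA issue is an ambiguous reference value with no stated progression date.

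The size is uncertain. On an assumed 12-month exponential median, censoring deaths adds about 0.6, 1.3 or 3.0 months at assumed death shares of 5, 10 or 20%. The direction of that part is known (the median is overstated), but the shift is smaller than the sampling error expected in this trial. The net effect of all three gaps is unknown.

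A reader might infer that the trial's main conclusions are at risk. They are not: dose assignment, the MTD and the success rule in 11.6.1 use only DLT and PSA response, and the sample size of 35 does not rest on PFS.

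**What to change.** 1. **7.2.6:** define PFS as the time from start of treatment to the first of progression or death from any cause. Censor patients who are alive and event-free at their last adequate assessment.
2. **11.2.2:** define rPFS (imaging progression or death) and PSA-PFS (PSA progression or death) in the same way, and keep time to PSA progression as the version without death.
3. **7.2.6 and 7.2.1:** cite 7.2.4 in 7.2.6 and write a bone exception into 7.2.1, so that one bone-scan rule and one date apply to both PFS and rPFS.
4. **7.2.3:** state which on-treatment value #2 refers to, what #4 must exceed, and which date is the progression date. Reconcile the section with 7.2.5, which refers to the smallest measurements since treatment started, and with 5.5, which ends treatment at disease progression. No PSA threshold, nadir rule or treatment rule is proposed here.

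The cost is wording plus a consistency check of 7.2.3 against 5.5. No new data are needed: section 6.0 already schedules PSA, imaging every 12 weeks and survival status, and 5.7 follows patients to death or 24 months after treatment. The downside is that the reported median PFS may be slightly shorter.
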